- Evaluate the clearance of SK's in off-face locations after removal using the Pulse TX System vs. pretreated appearance of the same lesion
- Evaluate the clearance of the treated SK's at various points in time over several weeks following the initial procedure, compared to the pre-treated SK's

PRIMARY ENDPOINT

- The primary endpoint of the study is the degree of clearing of benign SK lesions as rated by the independent reviewer's assessment of photographs of the lesions at the final study visit.
 - A 4-point scale (0, 1, 2, 3) will be used wherein each lesion will be characterized as "Clear", "Mostly Clear", "Partially Clear", "Not Clear".

Photographic Review of SK Lesions Rating Scale			
Clear	Mostly Clear	Partially Clear	Not Clear
0	1	2	3

○ See Attachment C for a protocol specific to the Independent Review.

SECONDARY ENDPOINTS

- A secondary endpoint of the study is the degree of clearing by the final visit as rated by the treating physician's assessment.
 - The same 4-point scale will be used as that used for the Photographic Review.

Investigator Assessment of SK Lesions Rating Scale			
Clear	Mostly Clear	Partially Clear	Not

			Clear
0	1	2	3

- An additional secondary endpoint of the study is subject satisfaction with the SK's area at the final study visit. A 5-point scale (0, 1, 2, 3 4) will be used wherein the Subject will be asked to rate their level of satisfaction with each SK area as "Satisfied", "Mostly Satisfied", "Partially Satisfied", "Dissatisfied" Highly Dissatisfied".

Patient Satisfaction for each SK area at day 106				
Satisfied	Mostly Satisfied	Partially Satisfied	Dissatisfied	Highly Dissatisfied (worse)
0	1	2	3	4

SUCCESS CRITERIA

- Independent Reviewer Assessment of Photograph: A score of "0" or "1" at the last follow-up will represent a successful outcome for that lesion. The study will be considered a success if 65% of treated lesions are reduced by a score of 2 or more points on the lesion scale
- Physician Assessment: A score of "0" or "1" at the last follow-up will represent a successful outcome for that lesion. Success for this criteria is 65% of lesions rated as a 0 or 1 on the scale.
- Patient Assessment: A score of "0" or "1" at the last follow-up will represent a successful outcome for that lesion. Success for this criteria will be 65% of lesion areas evaluated as "Satisfied" or "Mostly Satisfied".
- The overall study will be considered a success if 2 of the 3 criteria listed above are met.

STUDY DESIGN

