A prospective, randomized, open label, multi-site, NSR study design where each subject serves as his or her own control will be employed. A Principle Investigator will be identified at each of up to five participating sites. A total of up to 60 Subjects will be consented and enrolled with anticipated enrollment expected to be uniformly distributed across sites. The PI will consider the study inclusion and exclusion criteria and invite appropriate patients to participate in the study.

No significant risk is posed by either the use of the Pulse TX System or the study process. While safety can never be taken lightly, this study is not meant to measure, monitor or analyze any significant disease or disorder for which medical treatment is mandatory. (See additional information regarding Non-Significant Risk statement in the following pages.)

ANALYTICAL METHODS

Three sets of data will be analyzed:

1. Clinical observational data as derived from the examinations.
2. Data captured during the photograph review process.
3. Patient self-reported symptoms and observational data.

The statistical analysis for this single-arm NSR study will be performed after collection of safety, effectiveness and secondary outcomes during the baseline period and each evaluation interval.

- Analysis of primary endpoints in intent-to-treat population
- Analysis of primary and secondary endpoints in the per protocol population
- The calculation of the change from baseline in the treated lesion size and appearance will be adjusted by the observed effect on the untreated lesion change in size and appearance
- Exploratory Data Analysis to describe distributions and to explore trending
- Repeated measures ANOVA or non-parametric equivalent to compare means
- Likelihood ratio statistics to assess categorical data
- Chi-Square Tests to compare binary proportions
- Exact probabilities will be computed for any inferential analysis performed
- 95% confidence levels will be calculated using exact methods
- Agreement statistics to estimate the inter- and intra-photographic reviewer variability
- All analysis will be adjusted for the correlated nature of the data since more than one lesion is being sampled from the host subject

All tables and listings will be produced and stored in SAS datasets. No data imputations will be performed.

SAMPLE SIZE ESTIMATE

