A one group χ^2 test with a 0.050 two-sided significance level will have 91% power to detect the difference between the Null hypothesis proportion π_0 , of 0.510 (51%) and the Alternative proportion, π_A , of 0.650 (65%) when the sample size is 135.

DEVICE DESCRIPTION

[figure not shown]
The **Pulse TX System** consists of an electrical pulse generator (similar to devices used to electro-coagulate tissue) combined with a hand-piece which is held by the clinician during application of pulses to the skin surface. The hand-piece is coupled to a sterile, single patient-use treatment tip. The tip has an array of pins no greater than 1.27 mm in diameter (18 gauge) which penetrate the skin between 1 and 3 mm. Power settings within a minimum and maximum range are available for selection by the physician, and are software limited to defined setting for each treatment tip by the sponsor. Once the electrical pulse generator is turned on and a power setting is selected, a foot switch triggers a sequence of pre-programmed electrical pulses to an area of skin directly beneath the treatment tip.

A common commercially available sterile coupling gel is applied to the skin or treatment tip surface to ensure good electrical coupling to the tissue.

The three system components are as follows:

1. **Pulse Generator** including a built-in touch screen for setting selection, a power cord, and a mandatory foot pedal for activation of a pulsing sequence
2. **Hand-piece** (re-usable)
3. Single patient-use **Tip** (five different versions available, described below)

Pulse TX Graphic

Footswitch connector
Locking brakes

Figure 1. Pulse generator

[figure not shown]
Electrode Handpiece

A reusable handpiece allows the operator to connect the single-use patient treatment tip to the generator. One end of the handpiece connects to the generator; the other end connects to the treatment tip. The handpiece can be cleaned and after each use.

Single-use Treatment Tip

A sterile single-use patient Treatment Tip attaches to the hand-piece. The tip delivers the nano pulses to the area to be treated through an array of micro-needles. Five tip sizes are available:

- 2.5 mm x 2.5 mm Treatment tip
- 5 mm x 5 mm Treatment Tip
- 7.5 x 7.5 mm Treatment Tip
- 10 mm x 10 mm Treatment Tip

SITE/INVESTIGATOR SELECTION

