Up to 5 study sites will be selected to participate in the study. Two of the five sites have been identified. The additional sites have not yet been determined. The table below provides additional information

NAME OF STUDY SITE	ADDRESS OF STUDY SITE
Site 1: Aesthetic Artistry Surgical and Medical Center or AASMC	[name] T [contact]
[name] [name]	[name] T [contact]
Site 2: Aesthetic Center [name] [name]	[name] T [name]
Same Investigators at alternate location	[name] [contact] T [name]
TBD	
NAME OF STUDY MONITOR	
[name], MSN Consultant, Pulse Biosciences	[name] T [name] F [name] [contact]

Site #1 above will be the first to initiate the study. This site and the Investigators have been approved by BioMed for a study that is currently open but not active. The required forms and information about subsequent sites and Investigators will be provided to BioMed prior to any study related activities at the site in question. Prior to enrolling a Subject at any particular site the investigator and appropriate members of the study team at that site will participate in a comprehensive training program designed by Pulse.

SUBJECT RECRUITMENT AND SELECTION

Convenience sampling will be used to enroll subjects exclusively from the patient population at each of the sites. The planned enrollment is set at up to 15 subjects at each site for a total of 60. Recruitment will be conducted via direct communication between potential Subjects with each PI and/or the designated staff.

The invitation to participate will be extended to those patients who are known or present with SK lesions that they individually choose to have removed. The Informed Consent discussion and signature process will be conducted by the PI and/or the designated staff. Once consented, each Subject will be assigned a unique Study Identification Number. See Attachment D for statistical discussion and analysis of proposed Subject population.

Recruitment Statement

If recruitment is not adequate to meet the study requirements, a counter card or other media format may be used. See Attachment D for a proposed recruitment statement. The study **Inclusion** and **Exclusion** criteria are noted below.

Inclusion Criteria:

- Willing to sign the informed consent
- Males or females

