A Photographic Review Study was performed including images of 150 non-thermal lesions that were created among the enrolled Subjects. For each of these 150 lesions, specific characteristics associated with normal wound healing were evaluated and rated according to a predetermined scale. This Photographic Review Study was executed according to a comprehensive Protocol including Pre Training and followed by Intra- and Inter-rater analysis. The described Independent Photographic Review Study serves as a model for the proposed Photographic Review SK Study.

PURPOSE of the PHOTOGRAPHIC REVIEW

The independent review of the lesions photographed at each evaluation interval is being conducted to standardize the interpretation of the lesion clearance and appearance over time. The centralized independent review of the photographs can also reduce potential bias in these types of clinical trials where the assessment of the images can be subjective. Ensuring consistency and lack of bias is a critical issue for the Sponsor and FDA. The image acquisition and interpretation protocols help standardize the process across the clinical sites. A central review allows an auditable, rigorous, and uniform process of evaluation, thus achieving higher confidence in the integrity of the data.

OBJECTIVES and SUCCESS CRITERIA

1st objective is to confirm that reported ratings are reproducible over time when considering one reviewer's ratings at two different times so the agreement between the two time intervals should be at least 80%

2nd objective is to confirm that reported ratings are reproducible when considering responses among 3 reviewer's ratings when each is compared to the other two so the agreement between and among the reviews should be at least 80%

REVIEWER SELECTION

Not affiliated with the study

2-3 reviewers qualified by experience with evaluating skin lesions and wound healing

Multiple locations

Independent of each other

PHOTOGRAPH SELECTION & SET UP

- For each lesion in each of the 60 patients, five post-treatment photos of that lesion will be printed in a randomized order, along with an identified baseline photograph of that same lesion. Consistent standard of photographic analysis to select all images to be reviewed at all time points according to uniform criteria
- Images will be masked to time interval, energy settings, size of treatment tip, and specific subject identifiers.

STUDY PROCESS

MATERIALS NEEDED

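### The 91% power at 135 holds for independent observations, not for the correlation-adjusted analysis of three lesions per subject that the plan requires

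*Combined protocol and SAP*

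**What the plan says.** The Sample Size Estimate section is one sentence. It takes a one-group chi-square test at a two-sided 5% level, a null proportion of 51% and an alternative "of 0.650 (65%) when the sample size is 135", and gives 91% power. It does not say what the 135 units are, and it states no ICC, design effect or expected loss.

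Other sections fix the structure of the data:

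- Success Criteria counts lesions: "The study will be considered a success if 65% of treated lesions are reduced by a score of 2 or more points".
- Study Procedure has exactly three of four selected lesions treated in each subject, with the fourth as untreated control.
- Study Design caps enrolment: "A total of up to 60 Subjects will be consented and enrolled". Subject Recruitment and Selection repeats it: "The planned enrollment is set at up to 15 subjects at each site for a total of 60". Attachment C also works from this figure: "For each lesion in each of the 60 patients".
- Analytical Methods commits to an adjustment: "All analysis will be adjusted for the correlated nature of the data since more than one lesion is being sampled from the host subject". The same list keeps chi-square tests for binary proportions and adds "95% confidence levels will be calculated using exact methods". It also rules out imputation.
- Subject Recruitment and Selection refers onward: "See Attachment D for statistical discussion and analysis of proposed Subject population". Attachment D as supplied holds only a recruitment statement.

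**The concern.** A power figure should describe the test that will be run. Three lesions on one person share skin type, operator and healing, so their outcomes may well be alike, and the plan itself treats them as correlated. If they are, 135 lesions carry less information than 135 independent observations, and a test that allows for this has less power than the unadjusted formula gives.

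The sentence is the only sample-size justification in the supplied text. As it stands, a reader cannot tell what power the planned enrolment gives for the planned analysis, or how much loss to follow-up it can absorb.

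**Working it through.** **Inputs from the documents.** Null 0.51, alternative 0.65, two-sided 5%, n = 135 (Sample Size Estimate); 3 treated lesions per subject (Study Procedure); at most 60 subjects (Study Design).

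**Assumed inputs.** The documents give no ICC and no loss rate. I use ICC from 0.05 to 0.5, and either no loss or 10% of subjects lost.

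**Step 1: the unit.** 135 exceeds the cap of 60 subjects, so it cannot count subjects. 135 / 3 = 45 subjects, and 60 × 3 = 180 lesions is the maximum.

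**Step 2: reproduce the stated figure.**

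Power = Φ[(√n × 0.14 − 1.96 × √(0.51 × 0.49)) / √(0.65 × 0.35)]

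At n = 135: (1.627 − 0.980) / 0.477 = 1.356, and Φ(1.356) = 0.912. The stated 91% is this formula for independent observations, with nothing built in for clustering.

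**Step 3: allow for clustering.** With three lesions per subject the design effect is 1 + 2 × ICC, and the effective sample size is n / (1 + 2 × ICC). At 135 lesions and ICC 0.2 this is 135 / 1.4 = 96.4. Putting the effective size into the Step 2 formula gives:

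| ICC (assumed) | 135 lesions (45 subjects) | 162 lesions (54 subjects, 10% loss) | 180 lesions (60 subjects, no loss) |
|---|---|---|---|
| 0 | 91.2% | 95.4% | 97.0% |
| 0.05 | 88.4% | 93.4% | 95.6% |
| 0.1 | 85.5% | 91.2% | 93.8% |
| 0.2 | 79.6% | 86.5% | 89.9% |
| 0.3 | 74.0% | 81.6% | 85.5% |
| 0.5 | 64.0% | 72.2% | 76.7% |

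**Step 4: how far the margin of 45 lesions goes.**

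- An effective size of 135 needs 1 + 2 × ICC = 180/135, so ICC = 0.167 with no loss; with 162 lesions, ICC = 0.10.
- 80% power needs an effective size of 97.3. This is reached at ICC 0.19 with 135 lesions, 0.33 with 162 and 0.42 with 180.
- The loss that 60 subjects can absorb at an effective 135 is 1 − 45 × (1 + 2 × ICC)/60: 25% at ICC 0, 17.5% at 0.05, 10% at 0.1 and none at 0.167.

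**Step 5: the observed-65% rule.** The smallest observed proportion significant against 51% is 0.51 + 1.96 × √(0.51 × 0.49 / effective n). It rises to 65% only when the effective size falls to 49.0. That needs an ICC of about 0.88 at 135 lesions, and one above 1 (impossible) at 162 or 180.

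**Step 6: simulation check.** Beta-binomial data were analysed with a t test on subject proportions, 60,000 runs per cell. Power at ICC 0.05, 0.1, 0.2, 0.3 and 0.5 was:

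- 45 subjects: 88.2, 84.7, 79.2, 73.8 and 64.4%
- 54 subjects: 92.8, 90.5, 85.5, 80.6 and 72.1%
- 60 subjects: 95.1, 93.3, 89.3, 84.8 and 76.6%

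The two-sided error rate at 51% was 4.9 to 5.2%. The formula is thus optimistic by about a percentage point at most for this test.

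**The case against.** The strongest reply is that the design already holds a margin. Up to 180 treated lesions are planned against 135, and the text does not exclude 135 as an effective or minimum evaluable number. On that reading 91% is unexplained rather than wrong. The size of the margin stands, and it is substantial. But nothing in the supplied text calls 135 an effective or evaluable size, or links it to 60 subjects. The margin covers 25% loss at ICC 0 or an ICC of 0.167 at no loss, not both. Enrolment is also a ceiling, and with no imputation each lost subject removes up to three rated lesions. Even on the effective-size reading, the ICC and loss behind the figure are missing.

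A second reply is that Attachment D may hold the discussion. It may, and that limits this point. An ICC stated there would show which row of the table applies, but 91% would be the clustered power at 135 lesions only if that ICC were about zero.

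Three stronger readings are tempting and are not supported:

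- *The trial is underpowered.* At 60 subjects with no loss, power stays at or above 80% up to an ICC of about 0.42; with an assumed 10% loss, up to about 0.33.
- *The success rule is compromised.* That rule rests on an observed 65%, not on the test against 51%, and an observed 65% clears the adjusted test at any ICC with 162 or 180 lesions.
- *The plan abandons or misapplies the chi-square test.* Analytical Methods keeps chi-square tests and requires adjustment of all analysis. The form of the adjusted test is unspecified, but the plan does not propose to ignore clustering.

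**Conclusion.** The concern holds in a limited form. For any positive ICC, the stated 91% is not the power of the planned adjusted test at 135 lesions; at assumed ICCs of 0.1, 0.2 and 0.3 it overstates that power by about 6, 12 and 17 percentage points. For the full 60 subjects with no loss, power lies between about 96% and 77% over ICC 0.05 to 0.5, and the supplied text does not say where in that range the trial sits.

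This rests on 135 being a raw lesion count, the only count that fits the supplied text; on a common ICC with three rated lesions per subject; and on ICC and loss values that are mine. The defect is in the justification. It gives no ground for enrolling more patients.

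**What to change.** Restate the Sample Size Estimate with the treated lesion as the unit, up to 60 subjects and up to 180 treated lesions, the sponsor's own ICC and expected loss with a reason for each, the effective size n / (1 + 2 × ICC), and the resulting power. For example:

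> The unit of analysis is the treated lesion. Up to 60 subjects with three treated lesions each give up to 180 lesions. Assuming that 10% of subjects have no final-visit rating (54 subjects, 162 lesions) and an ICC of 0.2 (design effect 1.4, effective size 115.7), a two-sided 5% test of the lesion success proportion, adjusted for clustering by subject, has about 86% power to detect 65% against 51%. At an ICC of 0.05, 0.1, 0.3 or 0.5, power is about 93%, 90%, 81% or 72%.

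These power figures are for a subject-clustered t test, by simulation. The 10% and 0.2 are placeholders for the sponsor's values.

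In Analytical Methods, name the cluster-adjusted test and interval for this proportion, say how they fit with the exact-methods items, and compute the stated power for that same method. The clustered t test is one option; another would serve equally well if the power statement matches it. If the discussion cited in Attachment D exists, supply it and make it agree.

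The cost is wording in two sections and code for one test, with no extra patients. The stated power becomes somewhat less favourable (about 86% rather than 91% in the example), and the sponsor must commit to an ICC and a loss rate.

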- At least 18 years of age but less than 65 years of age
- Has a clinical diagnosis of stable, clinically typical seborrheic keratosis
- Medically determined candidate for at least 4 off-face SK lesions
- Must have at least four treatable SK's and be willing to have Pulse TX treatments on any three of the four treatable SK's. Treatable SK's must:
 - be at least 1 mm in height, and no greater than 3 mm in height.
 - not have a dimension perpendicular to the longest dimension of greater than 7.5mm or longer in any dimension than 20mm..
- Willing to have three of the designated SK's treated in a single treatment session
- Willing to return to the PI's office for five additional study visits at specified intervals over 106 days
- Agrees to high resolution photos of both the treated SK lesions and the untreated SK lesion
- No subject identity will be possible via the "lesion-only" photograph
- Has no evidence of active infection in the designated tissue prior to treatment

- Is not allergic to Lidocaine or Lidocaine-like products
- Not pregnant or lactating
- In the investigators' opinion, be in good general health and unlikely subject to risks from treatment

Exclusion Criteria:

- Implantable electronic devices. e.g., automatic defibrillator
- Active infection or history of infection within 90 previous days in designated test area
- Not willing or able to sign the Informed Consent
- Non English speaking or reading
- Is known to be immune-compromised
- Known to be keloid producer
- On blood thinning medications
- Diseases, conditions, or situations wherein PI judges that the patient is not appropriate for participation in the study

NON SIGNIFICANT RISK STATEMENT

The proposed study fits the criteria for a non-significant designation for the following reasons:

- Subjects will be recruited for the study strictly on a voluntary basis
- Participation in the study takes approximately 1 hour for the first treatment visit and 30 minutes for each of the five post treatment evaluation visits, which includes photographs of both treated and control lesion(s)
- Localized anesthesia will be used to control discomfort at the time of the test device application.
- After the test device is deployed and the anesthesia is dissipated, there may be mild, localized discomfort at the site of the treatment. A small scab or crust may develop. This occurrence is transient and should resolve without intervention.

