- Transient and minor discomfort at the treated site and appearance of a small scab typically occurs when other standard treatments are used, i.e., cryogen to remove SK's. Use of the Pulse TX does not raise any additional concerns compared to current methods of lesion removal
- There is no loss of privacy as no study records will be viewed or retrieved by anyone other than the study team members.

- Protected information will not be captured
- Subjects are protected by a coding system to de-identify them

STUDY PROCEDURE

The following is an example of the Subject related activities to be completed for each Subject in the study. The exact order may differ depending on Subject/PI schedules and preferences.

Activities prior to or on same day as study enrollment and occur on same day as treatment visit:

- evaluation for Inclusion/Exclusion criteria
- sign the consent form prior to any study activities
- receive a copy of the signed consent form

Activities on 1st Study Visit Day

- Four SK's are selected that meet the study criteria for treatable SK's. If more than four lesions are present, the patient can state a preference for which 4 lesions are included in the study
- Photographs of each of the four selected SK's will be taken prior to anesthesia or treatment
- Local anesthesia will be applied to the four selected SK's.
- Using a randomization method, exactly three of the selected SK's will be designated to be treated and one will be designated as an untreated control
- The test device will be deployed to the selected SK's according to the randomized order
- a light bandage will be applied
- Subject will be discharged

Activities on 2nd, 3rd, 4th, 5th and 6th Study Visit Days

- Photographs of each of the 3 treated lesions and one non-treated lesion will be taken
- Each lesion will be clinically assessed and the appearance will be rated according to specified criteria.
- Any adverse events will be identified and documented.

RANGE OF DAYS FOR STUDY VISIT INTERVALS		
STUDY VISITS	TARGET VISIT DATES	VISIT DATE RANGES
1	Treatment Day	NA
2	1 week post TX	7 to 9 days post TX
3	1 month post TX	28 to 35 days post TX
4	60 days post TX	50 to 60 days post TX
5	90 post TX	80 to 90 days post TX
6	106 days post	100 to 111 days post

SUBJECT COMPENSATION

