Epidermal Changes: Review of the changes of the entire thickness of the epidermal/dermal layer and subcutaneous fat from day 1 through day 60 was performed. The primary changes due to the non-thermal energy exposure were observed in the treated skin within the epidermal layer of skin. At day one post-treatment, tissue samples from all subjects showed evidence of "ghost cells" in the epidermal layer characterized by intact cell membranes and absence of nuclei within those cells, which indicates a non-viability of those cells. The non-viability of epidermal cells was full-thickness and complete for all energy settings by 1 day post-treatment. In many patients, hair follicles and eccrine glands within the dermal layer of the skin were also visible for histologic review. In specimens in which hair follicles and eccrine ducts were visible, there is partial (50%) to full necrosis of the upper portions of the hair follicles and eccrine ducts. 5 days post-treatment epidermal changes range from 50% to 90% healing (50% - 90% viable epidermal cells). Hair follicles and eccrine ducts when visible in the tissue samples show focal dyskeratotic cells within the hair follicles at 5 and 15 days consistent with partial healing at 5 days and complete recovery by 15 days. Eccrine ducts often showed focal squamous metaplasia, a sign of re-epithelialization. By 15 days the epidermis layer had returned to normal in almost all cases. By 60 days the epidermis, hair follicles, and eccrine glands had all completely returned to normal. Of note in two patients treated at the highest energy level, epidermal necrosis was followed by a formation of an inflammatory eschar. This formation healed by 60 days with some epidermal flattening and minimal papillary dermal fibrosis.

Alterations of dermal collagen: Alterations in the dermal collagen observed were minimal, with no evidence of thermal injury. In several tissue samples exposed to treatment levels five and six, there was focal papillary dermal necrosis evident. This effect was observed at the 1 day and 5 day intervals, but was not observed at the 15-60 day intervals. In two patients at treated at the highest energy level, there was some parallel fibrosis of the dermal collagen bundles at 60 days.

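### The activity schedule has no adverse-event step on treatment day and no active adverse-event or symptom collection before day 7 to 9, although Analytical Methods has safety collected from baseline and symptoms analyzed

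*Combined protocol and SAP*

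**What the plan says.** Study Procedure itemizes treatment day: lesion selection, photographs, local anesthesia to all four lesions, randomization, device use, a bandage, and finally "Subject will be discharged". Adverse events are not mentioned. The next list, headed "Activities on 2nd, 3rd, 4th, 5th and 6th Study Visit Days", has photographs, a clinical assessment and rating of each lesion, and "Any adverse events will be identified and documented". The visit table sets the first of these visits at "7 to 9 days post TX". No telephone call, diary or visit is scheduled before it. The section opens with a qualifier: "The following is an example of the Subject related activities to be completed for each Subject in the study". It adds that the order may vary.

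Analytical Methods places safety collection in the baseline period as well as at each evaluation interval. Its third data set is "Patient self-reported symptoms and observational data". It gives no instrument or timing for symptoms.

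The Non Significant Risk Statement says: "After the test device is deployed and the anesthesia is dissipated, there may be mild, localized discomfort at the site of the treatment". It describes scabbing as transient. Study/Device Risks does not expect infection, bleeding or discomfort needing a prescription, and would treat any of them as an unanticipated adverse event. It tells subjects to contact the investigator about concerns or unforeseen events.

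**The concern.** The protocol's safety statements are mainly about the hours and days just after treatment: discomfort as the anesthetic wears off, bleeding at the pin sites, reactions to the anesthetic. The pins are up to 1.27 mm in diameter and enter the skin by 1 to 3 mm at three lesions per subject. An event of this kind may be over within hours or days. If the first scheduled enquiry comes a week later and is open-ended, brief events will tend to be under-recorded, and a low count could then reflect the timing of the question as much as the behavior of the device.

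The sponsor's earlier abdominal-tissue study reported sensation during treatment and discomfort after the lidocaine wore off. The sponsor has therefore treated these as outcomes worth reporting, yet this protocol has no step that collects them. The symptom part of the third data set has no defined source.

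**Working it through.** The plan gives no adverse-event rate or safety sample size, so there is no figure of its own to reproduce on this point. Its one power statement concerns lesion clearance and is not an input. The check is a comparison of sections plus simple subtraction and multiplication.

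**1. Time to first scheduled enquiry** (visit table in Study Procedure). Treatment is day 0 and visit 2 is day 7 to 9. The gap is 7 − 0 = 7 days to 9 − 0 = 9 days.

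**2. Exposure in the gap** (up to 60 subjects from Study Design; three treated lesions and four anesthetized lesions per subject from Study Procedure).
- Device-treated lesions: 60 × 3 = 180.
- Anesthetized lesions, including the untreated control: 60 × 4 = 240.

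These figures are the size of the study, not a count of missed events.

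**3. The two sections side by side.**
- Study Procedure: an adverse-event step at five of six visits, and none at the visit where anesthetic and device are used.
- Analytical Methods: safety collected from the baseline period. That period is not defined. If it includes treatment day, the two sections disagree. If it ends before treatment, neither section provides for active collection from treatment to visit 2.

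**4. Which early events have a route into the data?**
- Signs still present at day 7 to 9: yes, through the visit 2 photographs and lesion assessment.
- Events the subject chooses to report: yes, through the contact route in Study/Device Risks.
- Events resolved before visit 2 and not volunteered: only if remembered and mentioned in answer to a general enquiry.
- Events seen in the clinic on day 0: staff may notice them, but no listed step requires a record.

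The gap is the last two groups.

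**5. Symptom data.** The only patient-completed instrument described is the satisfaction scale at the final visit (Secondary Endpoints). It supplies patient-reported data but not symptoms.

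**6. What the histology adds** (Attachment B). At day 1: "The non-viability of epidermal cells was full-thickness and complete for all energy settings by 1 day post-treatment". At day 5, 50% to 90% of epidermal cells were viable. Both sampling points precede visit 2, so substantial tissue change lies inside the unobserved interval. Visit 2 falls 7 − 5 = 2 to 9 − 5 = 4 days after the day 5 sample and 15 − 9 = 6 to 15 − 7 = 8 days before the next one. Tissue status at visit 2 itself is therefore not documented.

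**The case against.** The strongest reply is that the protocol as a whole does not confine safety collection to visits 2 to 6. Analytical Methods includes the baseline period, the activity list is called an example, the study is to follow GCP, sponsor experts attend the treatment sessions, and case report forms are not among the documents. This stands in part. A reader might infer that adverse events are collected only from visit 2. That is true of the activity list but not of the whole document. Still, none of these passages gives a step, a start point or an instrument for treatment day, and the example wording is followed only by a remark about order.

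A reader might also infer that the first week is captured by recall alone. The documents do not support that: subjects can contact the investigator, and visit 2 includes an examination and photographs. But subject-initiated contact is passive, and expected discomfort or brief bleeding need not prompt a call.

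A third tempting reading is that most of the injury is over before anyone asks. The histology does not show this. It comes from normal abdominal skin at six energy levels, the earliest sample was at 10 hours, and there was none between days 5 and 15. Healing at day 5 was as low as 50%, and some perivascular inflammation with fibrin was seen through day 60. Microscopic viability is also not an adverse-event rate.

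Nor is the third data set wholly without a source, since satisfaction ratings partly supply it. What lacks a source is its symptom component.

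Finally, there is no safety endpoint, so no success criterion moves. This is correct and limits the weight of the point.

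**Conclusion.** The point holds in limited form. The schedule has no adverse-event step on treatment day and no active adverse-event or symptom collection for the following 7 to 9 days. This does not fit Analytical Methods, which has safety collected from baseline and symptoms analyzed. Early events that resolve before visit 2 and are not volunteered would rest on unstructured recall, in the period that the protocol's reassuring statements mainly concern.

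Up to 60 subjects and 180 treated lesions are exposed to the gap. The number of events missed cannot be derived from the documents, and none of the three success criteria is affected. The conclusion assumes that sites follow the activity list as written and that no unseen form adds an earlier check. It does not depend on the histology. It is worth correcting because the change is cheap and alters what is collected; harmonizing the wording alone would leave the early interval without active collection.

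**What to change.** Reconcile Study Procedure with Analytical Methods as follows.

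- **Start point.** State that adverse-event recording begins at the first anesthetic administration on visit 1.
- **Before discharge on visit 1.** Add a check for adverse events and discomfort.
- **At visit 2.** Add fixed questions about the time since treatment: bleeding, signs of infection, discomfort, and any prescription or unscheduled contact. Record each by lesion and with day of onset. Because the control lesion is also anesthetized, lesion-level recording helps separate device effects from anesthetic effects.
- **Analysis.** Name these answers as the symptom component of the third data set. Tabulate events on treatment day and from then to visit 2 separately from later events.

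The cost is protocol wording and a short form at two visits that already take place. The downside is that more minor events will be recorded. Treatment and the efficacy assessments are unchanged.
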